2.4.3 Biomarkers of EHE activity in patients treated with trametinib

Plasma CTGF levels may be a useful biomarker of EHE survival as CTGF is a secreted protein whose gene is an immediate downstream target of TAZ-CAMTA1 (Tanas et al., 2016). CTGF is secreted and binds to α IIb β 3 integrin on the cell surface, leading in an autocrine fashion to downstream activation of RAS and MAP kinase pathways. This signal transduction pathway drives TAZ-CAMTA1-mediated NIH/3T3 cell transformation. Inhibition of any portion of this pathway inhibits transformation. This pathway is summarized in Figure 2. Preliminary studies have shown that CTGF is produced at high levels and secreted into culture media by cells that express TAZ-CAMTA1.

CTGF is secreted by EHE and can be quantified in plasma from EHE patients using enzyme-link immunosorbent assay (ELISA). If trametinib results in EHE cell death and objective tumor response, we hypothesize that CTGF plasma levels will decline. Alternatively, if trametinib blocks growth of EHE by inhibiting MEK but does not result

in cell death, we expect CTGF plasma levels will remain unchanged because the production and secretion of CTGF is upstream of the RAS and MAP kinase pathways. Additionally, patients with advanced EHE have elevated c-reactive protein levels and erythrocyte sedimentation rate in the blood (unpublished observation) which may be related to tumor production of CTGF. Blood from patients will be obtained prior to starting trametinib, approximately 4 weeks and 6 months after start of treatment with trametinib, and at the time objective tumor response or progression is identified to explore the relationship between trametinib treatment, plasma levels of circulating CTGF, c-reactive protein levels and erythrocyte sedimentation rate. ELISA for CTGF quantification will be performed by a central reference laboratory and CRP and ESR will be determined by local CLIA-certified laboratories using standard methods.

2.4.4 Tumor volume

We hypothesize that a change in volume of EHE will correlate with EHE response to treatment. Analysis of change in tumor volume identified more patients than RECIST 1.1 with response and correlated with survival in a retrospective analysis of Ewing sarcoma treated with anti-insulin-like growth factor therapy (Koshkin et al., 2016). [name] has experience in determining tumor volume using Columbia University's semi-automated solid tumor segmentation software (Koshkin et al., 2016). Digital radiology files will be obtained from treating centers and sent to [name] for analysis. Tumor volume will be determined for up to 3 dominant lesions per patient and change in volume over time will be calculated. Tumor response by volume will be compared to response by RECIST 1.1 and correlated with survival. Based on prior studies, increase in tumor volume of 100% or more will be scored as progression and decrease in volume of 45% or more will be scored as response (Koshkin et al., 2016).

3. PATIENT SELECTION

3.1 Eligibility Criteria

- 3.1.1 Patients must have measurable disease, defined as at least one lesion that can be accurately measured in at least one dimension (longest diameter to be recorded for non-nodal lesions and short axis for nodal lesions) as ≥ 20 mm (≥ 2 cm) with conventional techniques or as ≥ 10 mm (≥ 1 cm) with spiral CT scan, MRI, or calipers by clinical exam. Baseline imaging must be obtained within 30 days of Day 1 of study. See Section 11 for the evaluation of measurable disease.
- 3.1.2 Patients must have histologically confirmed epithelioid hemangioendothelioma which is metastatic or locally advanced (unresectable), and tumor tissue (paraffin-embedded tissue block or tumor tissue on unstained glass slides) available for fusion FISH analysis at Cleveland Clinic. Patient tumor tissue stored in pathology archives may be used for fusion FISH; a new biopsy is not mandatory.

- 3.1.3 Patients must have evidence of disease progression per RECIST1.1 prior to enrollment or have evidence of cancer-related pain requiring symptom management with narcotic analgesics.
- 3.1.4 Because there is no established standard or approved drug therapy for treatment of EHE, patients previously untreated or treated with drug therapy for EHE are eligible. There is no limit on the number of prior regimens used to be eligible.
- 3.1.5 Age ≥ 15 years. EHE is very unlikely to arise before the age of 15 years.
- 3.1.6 ECOG performance status ≤ 2 (Karnofsky $\geq 60\%$, see Appendix A).
- 3.1.7 Life expectancy of greater than 6 months.
- 3.1.8 Able to swallow orally-administered medication and does not have any clinically significant gastrointestinal abnormalities that may alter absorption such as malabsorption syndrome or major resection of the stomach or small bowel.
- 3.1.9 All prior treatment-related toxicities must be CTCAE v5 grade ≤ 1 (**except alopecia**) at the time of enrollment.
- 3.1.10 Patients must have normal organ and marrow function as defined below within 2 weeks of patient registration (for blood results) and 30 days of registration for LVEF assessment:
 - Absolute neutrophil count (ANC) $\geq 1 \times 10^9/L$
 - Hemoglobin ≥ 9 g/dL, patients may receive transfusion to meet criterion
 - Platelets $\geq 75 \times 10^9/L$
 - Albumin ≥ 2.5 g/dL
 - Total bilirubin $\leq 1.5 \times$ institutional upper limit of normal (ULN). **NOTE:** patients with elevated bilirubin secondary to Gilbert's disease are eligible to participate in the study
 - Aspartate aminotransferase (AST) and alanine aminotransferase (ALT) $\leq 2.5 \times$ institutional ULN
 - Serum creatinine ≤ 1.5 mg/dL *OR* calculated creatinine clearance (Cockcroft-Gault formula) ≥ 50 mL/min *OR* 24-hour urine creatinine clearance ≥ 50 mL/min
 - Left ventricular ejection fraction (LVEF) \geq institutional lower limit of normal (LLN) by ECHO or MUGA
- 3.1.11 Criteria related to reproductive issues.

Trametinib can cause fetal harm when administered to a pregnant woman. Women of child-bearing potential and men must agree to use adequate contraception (hormonal or barrier method of birth control; abstinence) prior to study entry, during the study participation, and for four months after the last dose of the drug. Women of child-bearing potential must have a negative serum pregnancy test within 14 days prior to enrollment and agree to use effective contraception throughout the treatment period and for 4 months after the last dose of study treatment. Should a woman become pregnant or

suspect she is pregnant while she or her partner is participating in this study, she should inform her treating physician immediately.

3.1.12 HIV-Patients positive for human immunodeficiency virus (HIV) are NOT excluded from this study, however HIV-positive patients must meet the following criteria:

- A stable regimen of highly active anti-retroviral therapy (HAART)
- No requirement for concurrent antibiotics or antifungal agents for the prevention of opportunistic infections
- A CD4 count above 250 cells/mcL and an undetectable HIV viral load on standard PCR-based test

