11.1.1 Definitions

Evaluable for toxicity. All patients will be evaluable for toxicity from the time of their first treatment with trametinib.

Evaluable for objective response. Only those patients who have measurable disease present at baseline, have received at least one cycle of therapy, and have had their disease re-evaluated will be considered evaluable for response. These patients will have their response classified according to the definitions stated below. (Note: Patients who exhibit objective disease progression prior to the end of cycle 1 will also be considered evaluable.)

Evaluable Non-Target Disease Response. Patients who have lesions present at baseline that are evaluable but do not meet the definitions of measurable disease, have received at least one cycle of therapy, and have had their disease re-evaluated will be considered evaluable for non-target disease. The response assessment is based on the presence, absence, or unequivocal progression of the lesions.

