11.1.2 Disease Parameters

Measurable disease. Measurable lesions are defined as those that can be accurately measured in at least one dimension (longest diameter to be recorded) as ≥ 20 mm (≥ 2 cm) by chest x-ray or as ≥ 10 mm (≥ 1 cm) with CT scan, MRI, or calipers by clinical exam. All tumor measurements must be recorded in millimeters (or decimal fractions of centimeters).

Note: Tumor lesions that are situated in a previously irradiated area will be considered measurable only if demonstration of progression of the lesion has occurred following radiation.

Malignant lymph nodes. To be considered pathologically enlarged and measurable, a lymph node must be ≥ 15 mm (≥ 1.5 cm) in short axis when assessed by CT scan (CT scan slice thickness recommended to be no greater than 5 mm [0.5 cm]) or MRI. At baseline and in follow-up, only the short axis will be measured and followed.

Non-measurable disease. All other lesions (or sites of disease), including small lesions (longest diameter < 10 mm [< 1 cm] or pathological lymph nodes with ≥ 10 to < 15 mm [≥ 1 to < 1.5 cm] short axis), are considered non-measurable disease. Bone lesions, leptomeningeal disease, ascites, pleural/pericardial effusions, lymphangitis cutis/pulmonitis, inflammatory breast disease, and abdominal masses (not followed by CT or MRI), are considered as non-measurable.

Note: Cystic lesions that meet the criteria for radiographically defined simple cysts should not be considered as malignant lesions (neither measurable nor non-measurable) since they are, by definition, simple cysts.

‘Cystic lesions’ thought to represent cystic metastases can be considered as measurable lesions, if they meet the definition of measurability described above. However, if non-cystic lesions are present in the same patient, these are preferred for selection as target lesions.

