13.5.2 Evaluation of Response

All patients included in the study must be assessed for response to treatment, even if there are major protocol treatment deviations or if they are ineligible. Each patient will be

assigned one of the following categories: 1) complete response, 2) partial response, 3) stable disease, 4) progressive disease, 5) early death from malignant disease, 6) early death from toxicity, 7) early death because of other cause, or 9) unknown (not assessable, insufficient data).

All of the patients who met the eligibility criteria and took at least 1 dose of trametinib will be included in the main analysis of the response rate. Patients in response categories 4-9 will be considered to have a treatment failure (disease progression). Thus, an incorrect treatment schedule or drug administration does not result in exclusion from the analysis of the response rate.

REFERENCES

Agulnik, M., JL Yarker, SH Okuno, *et al.* (2013). An open-label, multicenter, phase II study of bevacizumab for the treatment of angiosarcoma and epithelioid hemangioendotheliomas. *Ann Oncol.* 24:257-2563

Balagula, Y., K. Barth Huston, K.J. Busam, *et al.* (2010). Dermatologic side effects associated with the MEK 1/2 inhibitor selumetinib (AZD6244, ARRY-142886). *Invest New Drugs.* 29:1114-1121.

Bekaii-Saab, T., M.A. Phelps, X. Li, *et al.* (2011). Multi-institutional phase II study of selumetinib in patients with metastatic biliary cancers. *J Clin Oncol.* 29:2357-2363.

Bendell, J., P. LoRusso, E. Kwak, *et al.* (2011). Clinical combination of the MEK inhibitor GDC-0973 and the PI3K inhibitor GDC-0941: A first-in-human phase Ib study in patients with advanced solid tumors. *AACR Meeting Abstracts.* Abstract LB-89.

Blumenschein, G.R., E.F. Smit, D. Planchard, *et al.* (2013). MEK114653: A randomized, multicenter, phase II study to assess efficacy and safety of trametinib (T) compared with docetaxel (D) in KRAS-mutant advanced non-small cell lung cancer (NSCLC). *J Clin Oncol.* 31:Abstract 8029.

Borthakur, G., J.M. Foran, T. Kadia, *et al.* (2010). GSK1120212, a MEK1/MEK2 inhibitor, demonstrates acceptable tolerability and preliminary activity in a dose rising trial in subjects with AML and other hematologic malignancies. *Blood (ASH Annual Meeting Abstracts).* 116:Abstract 3281.

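### Section 3.1.1 counts a lymph node of 10 mm short axis as measurable disease, while section 11.1.2 requires 15 mm and classes the same node as non-measurable

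*Combined protocol and SAP*

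**What the plan says.** - **Eligibility, 3.1.1.** A patient needs at least one accurately measurable lesion, with "longest diameter to be recorded for non-nodal lesions and short axis for nodal lesions". The size is 20 mm or more by conventional techniques, or 10 mm or more "with spiral CT scan, MRI, or calipers by clinical exam". Nodes are named but get no threshold of their own. The item ends with a pointer: "See Section 11 for the evaluation of measurable disease".
- **Disease parameters, 11.1.2.** "To be considered pathologically enlarged and measurable, a lymph node must be" 15 mm or more "in short axis when assessed by CT scan" or MRI. Nodes with a short axis of 10 to under 15 mm fall among the lesions that "are considered non-measurable disease". Target lesions are chosen from measurable lesions.
- **Evaluability, 11.1.1.** "Only those patients who have measurable disease present at baseline, have received at least one cycle of therapy", and have been re-evaluated, count as evaluable for response. The exception is for progression before the end of cycle 1.
- **Analysis set, 13.5.2.** The denominator for the response rate is set broadly: "All of the patients who met the eligibility criteria and took at least 1 dose of trametinib will be included in the main analysis". Unknown or not-assessable outcomes count as treatment failures.
- **Response categories, 11.1.4.** A complete response requires pathological nodes to fall below 10 mm short axis, whether target or non-target. The table for non-measurable disease offers complete response but no partial response. Confirmation at 4 weeks or more is required.

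**The concern.** The two sections give different answers to whether a node of 10 to under 15 mm is measurable. For a patient with no other measurable lesion, the answer decides how the primary endpoint can be scored.

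Read literally, the plan admits that patient, declares the patient not evaluable for response, and then puts the patient in the denominator of the response rate. What can be scored is lopsided. There is no partial response for non-measurable disease. A complete response, however, needs only a fall from somewhere in the 10–14 mm range to below 10 mm, a change of 1 to 5 mm in whole-millimetre readings. The site's own reading decides the primary outcome (13.1), so central review does not correct it.

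The success rule is four responses among 27 patients, so one or two patients whose outcome depends on coding or on a small measurement change can matter.

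**Working it through.** **Inputs.** From 13.1: uninteresting response rate 5%, target rate 20%; 13 patients in stage I, continue with at least 1 response; success with at least 4 responses among 27, which leaves 14 in stage II. The affected patients are assumed to be among these 27.

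**Step 1: reproduce the stated design.** The probability of declaring activity at response rate p is

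P(p) = Σ over x ≥ 1 of Bin(x; 13, p) × P(Bin(14, p) ≥ 4 − x).

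| Stage I responses x | p = 5% | p = 20% |
|---|---|---|
| 1 | 0.3512 × 0.0301 = 0.0106 | 0.1787 × 0.5519 = 0.0986 |
| 2 | 0.1109 × 0.1530 = 0.0170 | 0.2680 × 0.8021 = 0.2150 |
| 3 | 0.0214 × 0.5123 = 0.0110 | 0.2457 × 0.9560 = 0.2349 |
| 4 or more | 0.0031 | 0.2527 |
| Sum, unrounded | 0.0416 | 0.8011 |

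Early stopping at 5% is 0.95^13 = 0.513. The stated power of about 80% and stopping probability of 51% reproduce. The attained type I error is 4.16%, so the stated 5% is the ceiling. A grid search confirms 13/27 with these cut-offs as the minimax design.

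**Step 2: affected patients counted as failures.** Give k of the 27 a response probability of 0 and the others 20% (power) or 5% (type I error). Ranges cover how the k patients split between stages.

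| k | Power | Type I error |
|---|---|---|
| 0 | 80.1% | 4.2% |
| 1 | 77.2–77.9% | 3.6–3.7% |
| 2 | 74.0–75.5% | 3.2–3.3% |

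**Step 3: affected patients who can reach a spurious complete response.** Give k patients an assumed chance q of a *confirmed* spurious complete response and the others 5%.

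| Assumed q | k = 1 | k = 2 |
|---|---|---|
| 4–9% | 4.1–4.6% | 4.0–5.0% |
| 20–30% | 5.5–6.7% | 7.0–10.1% |

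The lower band is what a 20–30% chance per scan becomes if the first and confirmatory readings err independently: 0.20² = 0.04 and 0.30² = 0.09. The upper band applies if 20–30% is already the chance after confirmation, for example because reading errors are strongly correlated.

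**The case against.** **Section 3.1.1 points to Section 11, so careful sites will use 15 mm.** Some probably will. But the pointer concerns how measurable disease is evaluated, and 3.1.1 states its own definition and number. Registrars must verify the eligibility criteria before enrolment (4.3.2), and a 10 mm node satisfies the criterion as printed.

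**A reader might infer that such a patient has no chance of response.** The documents do not support that. The table for non-measurable disease in 11.1.4.3 includes complete response, and 11.1.4.2 lets a non-target node meet it below 10 mm. A zero chance holds only if the patient is coded not assessable or other non-target disease persists. Step 2 is therefore conditional on that coding.

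**A reader might also infer that type I error is pushed above 5%.** That is not established either. Scoring such a node as a target lesion would breach 11.1.2. A complete response also needs confirmation at 4 weeks or more (11.1.4.3), with confirmatory scans at 4 to 8 weeks (11.1), which reduces responses caused by reading error alone. With independent readings the error rate stays at or below about 5%. Correlated readings or repeated assessments would raise it. No passage supplies the chance itself.

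**The case may never arise.** This stands. It requires metastatic or unresectable disease with no other measurable lesion, and the documents give no rate. It limits the size of the point but does not remove the contradiction.

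**Conclusion.** The point holds as an internal contradiction in the definition of measurable disease, and confidence in that textual finding is high. Confidence in its numerical effect is much lower, because the number of affected patients, the way they would be coded and the chance of a confirmed spurious response are all assumptions.

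Node-only disease is probably uncommon. On the assumed range of 0 to 2 patients, the consequence runs from nothing to a loss of about 2–3 percentage points of power for one patient, or 5–6 for two, if they are counted as failures. A rise in type I error is possible but rests on the upper band in step 3. The correction should be made because the rule is wrong as printed and cheap to repair; the design's operating characteristics have not been shown to fail.

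**What to change.** In 3.1.1, state at least 10 mm longest diameter for non-nodal lesions by CT, MRI or calipers, and at least 15 mm short axis for nodes, to match 11.1.2. Alternatively, let 3.1.1 take its definition directly from 11.1.2 and give no number of its own.

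Section 13.1 already reports stage I fusion results, so patients have been enrolled under the present wording. The sponsor should check whether any entered on a node of 10 to under 15 mm alone, and state how each such patient counts in the response rate. That statement should also say which rule governs when 11.1.1 and 13.5.2 disagree, because that conflict can arise for other reasons than node size.

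The cost is one line of text and a review of baseline lesion records. The sample size, cut-offs, power (80.1%) and type I error (4.16%) do not change. The one downside is that the rare patient with only 10–14 mm nodes is no longer eligible; 11.1.1 already treats that patient as not evaluable for response.

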3.2 Exclusion Criteria

3.2.1 Prior systemic therapy with a MEK inhibitor

3.2.2 History of another malignancy.

Exception: Patients who have been disease-free for 3 years or patients with a history of completely resected non-melanoma skin cancer and/or patients with indolent secondary malignancies, are eligible. Consult the CTEP Medical Monitor if unsure whether second malignancies meet the requirements specified above.

3.2.3 History of interstitial lung disease or pneumonitis requiring supplemental oxygen or treatment with oral or intravenously administered corticosteroids.

3.2.4 Any major surgery, extensive radiotherapy, chemotherapy with delayed toxicity (e.g. doxorubicin), biologic therapy, or immunotherapy within 21 days prior to enrollment and/or daily or weekly chemotherapy (e.g. sunitinib, sorafenib and pazopanib) without the potential for delayed toxicity within 14 days prior to enrollment.

3.2.5 Use of other investigational drugs within 28 days (or five half-lives, whichever is shorter; with a minimum of 14 days from the last dose) preceding the first dose of trametinib and during the study.

3.2.6 Symptomatic or untreated leptomeningeal or brain metastases or spinal cord compression.

3.2.7 Have a known immediate or delayed hypersensitivity reaction or idiosyncrasy to drugs chemically related to trametinib, or excipients or to dimethyl sulfoxide (DMSO).

3.2.8 Current use of a prohibited medication. The following medications or non-drug therapies are prohibited:

- Other anti-cancer therapy while on study treatment. (note: megestrol [Megace] if used as an appetite stimulant is allowed).
- Concurrent treatment with bisphosphonates is permitted; however, treatment must be

initiated prior to the first dose of study therapy. Prophylactic use of bisphosphonates in patients without bone disease is not permitted, except for the treatment of osteoporosis.

- Because the composition, PK, and metabolism of many herbal supplements are unknown, the concurrent use of all herbal supplements is prohibited during the study (including, but not limited to, St. John's wort, kava, ephedra [ma huang], ginkgo biloba, dehydroepiandrosterone [DHEA], yohimbe, saw palmetto, or ginseng).

3.2.9 History or current evidence/risk of retinal vein occlusion (RVO).

3.2.10 History or evidence of cardiovascular risk including any of the following:

- A QT interval corrected for heart rate using the Bazett's formula QTcB \geq 480 msec.
- History or evidence of current clinically significant uncontrolled arrhythmias (Exception: patients with controlled atrial fibrillation for >30 days prior to randomization are eligible).
- History of acute coronary syndromes (including myocardial infarction and unstable angina), coronary angioplasty, or stenting within 6 months prior to randomization.
- History or evidence of current \geq Class II congestive heart failure as defined by the New York Heart Association (NYHA) functional classification system.
- Treatment-refractory hypertension defined as a blood pressure of systolic >140 mmHg and/or diastolic >90 mmHg which cannot be controlled by anti-hypertensive therapy.
- Patients with intra-cardiac defibrillators.
- Known cardiac metastases.

3.2.11 Known Hepatitis B Virus (HBV), or Hepatitis C Virus (HCV) infection (patients with chronic or cleared HBV and HCV infection are eligible).

3.2.12 Any serious and/or unstable pre-existing medical disorder (aside from malignancy exception above), psychiatric disorder, or other conditions that could interfere with subject's safety, obtaining informed consent or compliance to the study procedures.

3.2.13 Trametinib was embryotoxic and abortifacient in rabbits at doses greater than or equal to those resulting in exposures approximately 0.3 times the human exposure at the recommended clinical dose. Therefore, the study drug must not be administered to pregnant women or nursing mothers. Women of childbearing potential should be advised to avoid pregnancy and use effective methods of contraception. Men with a female partner of childbearing potential must have either had a prior vasectomy or agree to use effective contraception. If a female patient or a female partner of a patient becomes pregnant while the patient receives trametinib, the potential hazard to the fetus should be explained to the patient and partner (as applicable).

3.2.14 Inability to comply with protocol-required procedures.

